## **(8) Observation of adverse events**

Observation of adverse events: Clinicians should evaluate the fluid resuscitation of children at any time during the experiment. If the clinical symptoms and other auxiliary examinations ( such as heart rate, liver size, mental state, X-ray, blood gas analysis, etc. ) If they are inconsistent with the relevant non-invasive examinations, the experiment should be terminated immediately and the superior physician should be found in time to assist.

## **(9) Data security monitoring**

Clinical research will develop a corresponding data security monitoring plan based on the size of the risk. All adverse events were recorded in detail, properly handled and tracked until they were properly resolved or stable. Serious adverse events and unexpected events were reported to the ethics committee, competent authorities, sponsors and drug supervision and management departments in a timely manner according to the regulations. The main researchers regularly conduct a cumulative review of all adverse events, and if necessary, convene a meeting of researchers to assess the risks and benefits of the study; research that is greater than the minimum risk will arrange independent data monitors to monitor the research data, and high-risk research will establish an independent data security supervisory

committee to monitor the accumulated security data and effectiveness data to make recommendations on whether the research will continue.

## **(10)Statistical processing**

This study adopted a prospective randomized controlled design, and the sample size was estimated using PASS 15.0 software. Based on the difference in 6-hour fluid resuscitation volume between the two groups in the pilot study (mean difference 1261 mL, standard deviation 3155 mL),  $\alpha=0.05$  (bilateral) was set  $\beta=0.2$ , Calculated to require 27 cases per group, considering a 20% dropout rate, 60 cases were ultimately included. Use SPSS 26.0 to generate block random sequences (block size 4), and allocate concepts through sealed envelopes. The normality of the measurement data was confirmed by Shapiro Wilk test, and those that conform to the normal distribution were expressed as mean  $\pm$  standard deviation. Independent sample t-test was used for inter group comparison; non normally distributed individuals are represented by the median (interquartile range) and Mann Whitney U test is used. The categorical data is presented in terms of the number of cases (%), and the comparison between groups is conducted using the chi square test or Fishers exact test (when the theoretical frequency is less than 5). The main outcome (28 day mortality rate) was plotted using Kaplan Meier survival curve, and inter group differences were analyzed using log rank test, and HR (95% CI) was calculated. Secondary outcomes (such as fluid dosage, MAP, etc.) report mean difference (MD) or relative risk (RR) and their 95% confidence intervals. All tests are bilateral, and  $P<0.05$  is considered statistically significant. Perform Bonferroni correction on secondary outcomes ( $\alpha=0.05/6 \approx 0.008$ ). Multivariate Cox regression was used to adjust for confounding factors such as age and baseline lactate, and sensitivity analysis included protocol set (PP) and intention to treat (ITT) analyses. The statistical software used is R 4.3.1 (R Foundation) and SPSS 26.0 (IBM).

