# **Clinical research protocol**

Project name: The value of critical care ultrasound and noninvasive cardiac output monitoring in guiding fluid resuscitation for septic shock in the emergency department

leading unit:Guangzhou Panyu Central Hospital, Guangzhou, Guangdong, China

project leader:[name]

Department: Emergency Department

Research period: July 2025 to July 2025

Version No.: V 1.0

Version Date: May 22, 2023

|                                      |   |
|--------------------------------------|---|
| object name                          | The value of critical care ultrasound and non-invasive cardiac output monitoring in fluid resuscitation for emergency department patients with septic shock.  |
| goal of study                        | This study explores the value of critical care ultrasound and non-invasive cardiac output monitoring in fluid resuscitation for emergency department patients with septic shock, providing evidence for optimizing hemodynamic management of septic shock, improving patient prognosis, and guiding clinical selection of appropriate monitoring modalities.  |
| research design               | Subjects were recruited from patients with septic shock admitted to the Emergency Department of Guangzhou Panyu District Central Hospital between July 2023 to July 2025. Demographic data of patients, including gender, age, and underlying diseases, were collected, along with mean arterial pressure, baseline lactate levels, and vital signs at enrollment. Records were made of the total fluid volume administered within the first 6 hours after patients were randomized into groups, the achievement of resuscitation targets, blood lactate levels, blood pressure, and the incidence of complications such as pulmonary edema and renal injury. Additionally, the use of vasoactive agents (e.g., dopamine, epinephrine/norepinephrine), mechanical ventilation support, and antibiotics was documented. Patients were followed up to record the duration of emergency department stay, total hospital stay, 28-day mortality, and adverse events occurring during the study period (e.g., severe arrhythmias, anaphylactic shock). |
| Total number of cases studied | 60 cases (30 cases in each group)   |

|                            |   |
|----------------------------|---|

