## **(3) Research Design Types, Principles, and Test Procedures**

### **1. Research Design**

Subjects were recruited from patients with septic shock admitted to the Emergency Department of Guangzhou Panyu District Central Hospital between July 2023 to July 2025. Demographic data of patients, including gender, age, and underlying diseases, were collected, along with mean arterial pressure, baseline lactate levels, and vital signs at enrollment. Records were made of the total fluid volume administered within the first 6 hours after patients were randomized into groups, the achievement of resuscitation targets,

blood lactate levels, blood pressure, and the incidence of complications such as pulmonary edema and renal injury. Additionally, the use of vasoactive agents (e.g., dopamine, epinephrine/norepinephrine), mechanical ventilation support, and antibiotics was documented. Patients were followed up to record the duration of emergency department stay, total hospital stay, 28-day mortality, and adverse events occurring during the study period (e.g., severe arrhythmias, anaphylactic shock).

After patients met the inclusion criteria and signed the informed consent form, random numbers were generated using SPSS 26.0 statistical software to randomly assign 73 participants to the critical care ultrasound group and the non-invasive cardiac output group. The generated random allocation table was prepared in duplicate, which were sealed and stored by the statistician and research coordinator respectively to prevent premature disclosure of group allocation information.

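### The stated difference and SD need about 100 patients per group, not 27; power is then about 30%, not 80%, and the total of 60 neither covers 20% dropout nor agrees with the 73 randomised

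*Protocol*

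**What the plan says.** The only sample size justification is in Protocol section (10), repeated in the statistical method row of the synopsis.

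- **Endpoint for sizing:** "Based on the difference in 6-hour fluid resuscitation volume between the two groups in the pilot study".
- **Inputs:** "mean difference 1261 mL, standard deviation 3155 mL", two-sided alpha 0.05, beta 0.2 (80% power).
- **Test for normally distributed measurements:** "Independent sample t-test was used for inter group comparison", with Mann-Whitney U otherwise.
- **Result:** "Calculated to require 27 cases per group, considering a 20% dropout rate, 60 cases were ultimately included".

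The synopsis row for the total number of cases gives "60 cases (30 cases in each group"). Section (3), under Research Design, says that SPSS random numbers were used to "randomly assign 73 participants to the critical care ultrasound group and the non-invasive cardiac output group". No passage links the 73 to the 60.

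**The concern.** Detecting a difference of 0.4 SD with 80% power normally takes about 100 patients per group, so 27 looks wrong on sight. If the printed inputs are right, the trial has roughly a one-in-three chance of detecting the difference it was designed around, while the protocol implies four in five. A non-significant result on fluid volume could then be given more weight as evidence of no difference than the design supports.

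Two further figures fail to fit. A total of 60 leaves too little room above 54 (2 × 27) for 20% dropout. A count of 73 randomised cannot stand beside a planned total of 60, so it is unclear when recruitment should stop.

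**Working it through.** **Inputs** (Protocol section (10)): difference 1261 mL; SD 3155 mL; two-sided alpha 0.05; power 0.80; two independent groups. The 1:1 allocation comes from the synopsis (30 per group).

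**1. Trying to reproduce 27 per group**

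Standardised effect: d = 1261/3155 = 0.3997.

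Normal formula: n per group = 2(1.960 + 0.842)²/d² = 98.3, so 99. The noncentral t solution is 99.2, so 100 per group.

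The stated 27 is not reproduced. Other readings do not give it either:

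| Reading | n |
|---|---|
| Two-sided two-sample t-test (as stated) | 100 per group |
| One-sided two-sample t-test | 79 per group |
| Paired or one-sample t-test, two-sided | 52 |
| Paired or one-sample t-test, one-sided | 41 |
| 3155 read as the SD of a difference (3155/√2) | 51 per group |
| Power of only 50%, normal formula | 49 per group |

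Planning for Mann-Whitney makes the number larger: 99/0.955 = 103.7, so 104 per group under normality.

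**2. What would give 27**

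With 27 per group, 80% power needs d = 0.777. That means an SD of about 1623 mL with the difference at 1261 mL, or a difference of about 2451 mL with the SD at 3155 mL. Halving the SD (1577.5 mL) gives 26 per group, close to 27, but nothing in the protocol supports that value.

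**3. Power for fluid volume with the stated inputs** (noncentral t, two-sided 0.05)

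| Analysed per group | Source | Power |
|---|---|---|
| 24 | 30 less 20% | 27% |
| 27 | stated requirement | 30% |
| 30 | all 60 analysed | 33% |
| 36 and 37 | all 73 analysed | 39% |

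**4. Dropout, taking 27 as given**

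- Correct inflation: 27/(1 − 0.20) = 33.75, so 34 per group and 68 in total.
- The shortcut 27 × 1.2 = 32.4, so 33 per group, also exceeds 30.
- What 60 allows for: 1 − 54/60 = 10%.
- What 20% loss from 60 leaves: 48, or 24 per group, below the required 54.

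With 100 per group, the same 20% allowance would give 100/0.8 = 125 per group, 250 in total.

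**5. The 73**

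73 equals neither 60 nor 68. Losing 20% of 73 leaves 58; going from 73 to 60 is a loss of 13/73 = 17.8%.

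**The case against.** **The printed inputs may be wrong rather than the 27.** If the pilot SD was near 1620 mL and was mistranscribed, 27 per group and 80% power are right. This stands: the protocol cannot show which number is wrong, so the 30% is conditional on the printed inputs. It does not rescue the paragraph, because one printed figure must then be corrected.

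**Perhaps 73 were to be randomised and 60 retained.** The elimination criteria in section (4) do remove patients after enrolment, and 20% loss from 73 leaves 58, above 54. But the protocol never says this, and section (10) presents 60 as the number reached after allowing for dropout. The reading is possible but unsupported.

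**The power quoted is not for the primary outcome, nor at the level the protocol would apply.** Correct. Sections (7) and (10) name 28-day mortality as primary, the synopsis efficacy row names lengths of stay, and section (10) treats fluid volume as secondary with a Bonferroni level of 0.05/6. At that level the same inputs give about 13% power with 30 per group, a detectable difference of about 3090 mL with 27 per group, and a requirement of 154 per group. This makes the shortfall larger, and any restated power must name its endpoint and alpha.

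**A misread null result is not certain.** Fair. Section (10) promises confidence intervals and makes no equivalence claim. The risk lies in interpretation; the numerical error exists regardless.

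**Conclusion.** The concern holds. As printed, the inputs require 100 per group (99 by the normal formula) against 27 stated, a nearly fourfold gap that no standard variant closes. If the difference of 1261 mL and SD of 3155 mL are correct, power for fluid volume at two-sided 0.05 is 30% with 27 per group, 33% with 30 and 27% after 20% loss, against 80% claimed. These figures assume equal allocation, normally distributed volumes and a common SD.

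The dropout error is separate and stands even if 27 is accepted: 60 absorbs 10%, not 20%. The protocol also states two incompatible totals, 60 and 73. The sample size error alone makes this a must-fix.

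**What to change.** 1. Check the difference and SD against the pilot output and the PASS report.
   - **If 1261 mL and 3155 mL are correct:** remove the 27 per group and the implied 80% power. State that 30 per group gives about 33% power for fluid volume at two-sided 0.05 (about 27% after 20% dropout), or that 27 per group detects about 2450 mL with 80% power. Add that at the Bonferroni level of 0.05/6 power with 30 per group is about 13%.
   - **If an input was mistranscribed:** correct it and show the calculation again. With the difference unchanged, 27 per group implies an SD of about 1620 mL.
2. Correct the dropout statement. If 27 per group stands, either say that 60 allows for 10%, or keep 20% and plan 34 per group, 68 in total.
3. Give one number to be randomised in the synopsis and in sections (3) and (10). If 73 has a separate meaning, state it.

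The cost is protocol wording and a less favourable power statement. No extra patients are needed if the power is restated; keeping 80% power with the printed inputs would take about 100 evaluable patients per group.

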| case selection      | 
Inclusion criteria:
 
(1) diagnosis of septic shock in accordance with the Surviving Sepsis Campaign International; (2) receipt of initial fluid resuscitation in the emergency department with a hospital stay of at least 6 hours; (3) age <math>\geq</math> 18 years; (4) provision of informed consent.
 
excluded criteria:
 
(1) contraindications to rapid fluid administration (e.g., end-stage renal disease, end-stage heart failure, acute pulmonary edema); (2) inability to comply with treatment, such as patients with severe trauma, burns, cancer undergoing chemotherapy, pregnant or lactating women, and those with mental illness; (3) withdrawal from treatment or transfer to another facility within 24 hours of admission.
 |
| Treatment plan      | 
Both groups were managed according to the 2021 Surviving Sepsis Campaign (SSC) International Guidelines for septic shock resuscitation, including: (1) early antimicrobial therapy, (2) vasopressor support (with norepinephrine as first-line), and (3) organ function support. The key difference between groups lay in the fluid resuscitation monitoring approach (critical care ultrasound vs. noninvasive cardiac output monitoring)
   |
| efficacy evaluation | 
The main efficacy indicators: emergency department length of stay, total hospital stay.
 
Secondary efficacy indicators: regarding total fluid volume within the first 6 hours of resuscitation, early resuscitation efficacy (time to achieve mean arterial pressure <math>\geq</math>65 mmHg, lactate reduction <math>\geq</math>20% from baseline, or lactate clearance <math>\geq</math> 10%), complication rates (including pulmonary edema, renal injury, and acute respiratory distress syndrome).
   |

|                           |  |
|---------------------------|--|
|                           | Safety evaluation index: 28-day mortality.   |

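### A single fixed block size of 4, stated in the protocol of a one-department trial with visibly different arms, makes up to a third of assignments foreseeable to staff who track them

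*Protocol*

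**What the plan says.** Protocol section (10), Statistical processing, and the same text in the synopsis, fix the method: "Use SPSS 26.0 to generate block random sequences (block size 4), and allocate concepts through sealed envelopes". The words about concepts presumably mean allocation concealment. No second block size, stratification factor or central allocation is described.

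The synopsis plans "60 cases (30 cases in each group" in total. Section (3), Research Design, instead speaks of using random numbers "to randomly assign 73 participants to the critical care ultrasound group and the non-invasive cardiac output group".

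On custody of the list, section (3) says: "The generated random allocation table was prepared in duplicate, which were sealed and stored by the statistician and research coordinator respectively". It gives the purpose as "to prevent premature disclosure of group allocation information".

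Recruitment is from "patients with septic shock admitted to the Emergency Department of Guangzhou Panyu District Central Hospital between July 2023 to July 2025", so from one department. The synopsis describes the contrast between arms thus: "The key difference between groups lay in the fluid resuscitation monitoring approach (critical care ultrasound vs. noninvasive cardiac output monitoring". Masking of staff is not mentioned anywhere.

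**The concern.** In a permuted block of four with two places per arm, the last assignment always follows from the first three, and sometimes the last two follow from the first two. Such a block stays unpredictable only if staff do not know its size or cannot see past assignments. Here the size is written in the protocol. Past assignments can be seen at the bedside, because one arm has an ultrasound machine and the other has chest electrodes and a monitor screen. With a single department there is one sequence to follow.

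Under section (3), eligibility and consent come before assignment. A clinician who foresees the next arm could therefore let it influence whether or when a patient is approached. Some exclusion criteria leave room for judgement, such as contraindication to rapid fluids or inability to comply with treatment. If sicker patients are steered to one arm, the arms differ in severity at entry. That bears directly on 28-day mortality, which sections (7) and (10) name as the main outcome, and on length of stay. With 30 patients per arm, a few such decisions could matter.

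**Working it through.** The protocol states no predictability figure, so there is none to reproduce.

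**Inputs.** Block size 4 (section (10)); 1:1 allocation, 30 + 30 = 60 (synopsis), which is 60/4 = 15 complete blocks. Visible assignments are inferred from the devices and the absence of any masking.

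**Observer.** Knows the block size, sees every earlier assignment, and knows where each block starts. An assignment is certain once one arm's two places in the block are used. The best guess is the arm with more places left, or a coin toss when they are equal.

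**Enumeration of the six equally likely blocks.**

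| Block | Certain assignments | Expected correct guesses |
|---|---|---|
| AABB, BBAA | 2 each | 0.5 + 0 + 1 + 1 = 2.5 |
| ABAB, ABBA, BAAB, BABA | 1 each | 0.5 + 1 + 0.5 + 1 = 3.0 |

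- Certain: (2×2 + 4×1)/6 = 1.333 per block; 1.333/4 = 33.3%; 0.333 × 60 = 20 patients.
- Correct guesses: (2×2.5 + 4×3.0)/6 = 2.833 per block; 2.833/4 = 70.8%; 0.708 × 60 = 42.5 patients.
- If 73 are randomised, the first 72 make 18 blocks, with 18 × 1.333 = 24 certain assignments.

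The fourth place in every block is certain; the third is certain in one third of blocks.

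**Varied block sizes, same kind of observer.** The sizes are drawn at random with equal probability. The observer sees the full history and knows the set of sizes but not their order. Simulation of 20,000 lists of 60:

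| Scheme | Certain | Of 60 | Best guess correct |
|---|---|---|---|
| Fixed 4 | 33.3% | 20 | 70.8% |
| Random 4/6 | 5.6% | 3.4 | 69.0% |
| Random 4/6/8 | 2.3% | 1.4 | 67.8% |

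Smaller simulations gave 2.2% and 2.4% for 4/6/8, so 2% to 2.5% is a fair statement. By enumeration, one larger fixed block helps much less: size 6 leaves 25% certain and size 8 leaves 20%.

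**A weaker observer.** For someone who follows only the running difference between arms, certain assignments are 8.3% with fixed blocks of 4, 1.0% with 4/6, and about 0.2% with 4/6/8. These figures may be compared with each other, not with the 33.3%. The best-guess figures are the same for this observer, since choosing the arm that is behind is already the best rule.

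**Cost in balance.** In the same 4/6/8 simulation, the arms at 60 patients were equal in 73% of lists, differed by 2 in 27% and by 4 in 0.4%. Complete blocks of 4 always end equal.

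**The case against.** A fixed block of 4 is a common choice and contradicts nothing in the protocol. One third is an average for an attentive observer. Over a planned two years, 60 to 73 patients is about 2.5 to 3 a month (60/24 to 73/24), and several enrolling clinicians would each have to keep the count. Both arms are active monitoring, so a motive to steer is not evident, and septic shock leaves little time to delay. Mortality is objective, and a Cox model adjusting for factors such as age and baseline lactate is planned. Varying the blocks lowers best-guess accuracy by only three percentage points. Section (12) refers to a randomisation plan that is not shown and may hold further safeguards.

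Most of this stands as a limit on size. It does not remove the point: following one sequence in one department is feasible, an objective outcome does not protect against selection at entry, and adjustment for a few measured factors cannot restore balance in unmeasured severity.

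Three stronger readings are tempting but unsupported:

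- **That enrolling staff did know a third of assignments.** The protocol states the block size, but nothing shows who read it and when, or that it was public during recruitment.
- **That the coordinator could consult the list.** Both copies were sealed, expressly to prevent early disclosure, and the coordinator is not said to enrol patients. All that can be said is that separation from enrolment is not stated.
- **That varied blocks cut certainty from 33% to under 1%.** This sets a full-history figure against one for the weaker observer.

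**Conclusion.** The point holds as a weakness in a stated design choice, worth correcting at small cost; it is not evidence of bias. An observer with the full history can determine 33.3% of assignments (20 of 60) and guess 70.8% correctly. This rests on 1:1 blocks of 4 without strata, visible assignments (an inference, though a safe one given the devices), and staff who know the block size and follow block boundaries. Without that tracking, fewer assignments are certain.

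Varying the block sizes removes most of the certainty but little of the guessability, so some risk of selective enrolment remains in any unmasked, blocked, single-department trial. Custody of the second list is a minor, separate point.

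Whether the design can still be changed is unclear. The synopsis and sections (3) and (12) end recruitment in July 2025, while section (5) gives December 2022 to January 2026.

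**What to change.** 1. For any sequence still to be issued, regenerate the list with randomly varied block sizes, for example 4, 6 and 8.
2. Replace the block size in the synopsis and section (10) with a statement that permuted blocks of varying size are used, and keep the sizes in a restricted randomisation file.
3. Have the duplicate list held by someone with no part in enrolment, and say so in section (3).
4. If no sequence remains, report the fixed block of 4 as a limitation and show baseline severity by arm.
5. Reconcile the number randomised (60 or 73) and the recruitment dates, which decide whether items 1 and 2 still apply.

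The cost is a new list for the unissued part, a short wording change, and a slightly larger possible final imbalance, usually 0 or 2 patients and rarely 4 in 60.

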#### **(4) case selection**

##### 1. Inclusion criteria:

(1) diagnosis of septic shock in accordance with the Surviving Sepsis Campaign International; (2) receipt of initial fluid resuscitation in the emergency department with a hospital stay of at least 6 hours; (3) age  $\geq 18$  years; (4) provision of informed consent.

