##### 2. Excluded criteria:

(1) contraindications to rapid fluid administration (e.g., end-stage renal disease, end-stage heart failure, acute pulmonary edema); (2) inability to comply with treatment, such as patients with severe trauma, burns, cancer undergoing chemotherapy, pregnant or lactating women, and those with mental illness; (3) withdrawal from treatment or transfer to another facility within 24 hours of admission.

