### **(6) Observation items and detection time points**

1. Demographic data of patients, including gender, age, and underlying diseases, were collected, along with mean arterial pressure, baseline lactate levels, and vital signs at enrollment.
2. Records were made of the total fluid volume administered within the first 6 hours after patients were randomized into groups, the achievement of resuscitation targets, blood

lactate levels, blood pressure, and the incidence of complications such as pulmonary edema and renal injury.

3. Document the use of vasoactive agents (e.g., dopamine, epinephrine/norepinephrine), mechanical ventilation support, and antibiotics.
4. Record the duration of Emergency Department stay, total hospital stay, 28-day mortality, and adverse events occurring during the study period (e.g., severe arrhythmias, anaphylactic shock).

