## **(7) standards for efficacy appraisal**

The primary outcome was 28-day mortality

Secondary outcomes included the efficacy of initial resuscitation, duration of hospital stay, incidence of complications, and other relevant parameters.

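### Total hospital stay is compared with no rule for deaths, so an arm with more early deaths tends to show the shorter stay

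*Protocol*

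**What the plan says.** Section (10) of the protocol, repeated in the synopsis, sends every continuous variable through a Shapiro-Wilk test. If normality holds, "Independent sample t-test was used for inter group comparison"; otherwise medians are given and Mann-Whitney is used. For secondary outcomes the plan is to "report mean difference (MD) or relative risk (RR) and their 95% confidence intervals". Survival methods are reserved for death: "The main outcome (28 day mortality rate) was plotted using Kaplan Meier survival curve", with a log-rank test and a hazard ratio.

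Hospital stay has two roles. The synopsis states "The main efficacy indicators: emergency department length of stay, total hospital stay". Section (7) makes 28-day mortality primary and then says "Secondary outcomes included the efficacy of initial resuscitation, duration of hospital stay, incidence of complications, and other relevant parameters". In either role, stay is a continuous measurement and takes the t-test or Mann-Whitney route.

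Section (6) collects stay and death as separate items: "Record the duration of Emergency Department stay, total hospital stay, 28-day mortality". No rule links them. Two eligibility rules touch on length of stay, "receipt of initial fluid resuscitation in the emergency department with a hospital stay of at least 6 hours" and the exclusion for "withdrawal from treatment or transfer to another facility within 24 hours of admission", but neither deals with death in hospital. The elimination, suspension and withdrawal criteria do not either.

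**The concern.** A hospital stay ends either in discharge alive or in death, and a raw count of days treats the two alike. An early death then looks as good as a very fast recovery. Leaving deaths out does not solve this, because survival is itself affected by treatment and the survivors of the two arms are no longer randomised groups.

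Deaths are unlikely to be rare. Section (1) cites mortality above 40% in septic shock; that is a background figure, not a design assumption. The trial's aim includes guiding the choice of monitoring method, and the synopsis ranks stay among its main efficacy indicators. A shorter stay would naturally be read as favouring that arm's monitor, even if it came from more patients dying early.

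**Working it through.** The protocol gives no figure for hospital stay or time to death, so there is nothing of its own to reproduce. The check asks how large a difference in stay arises from mortality alone when survivors' stay is the same in both arms.

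**Formula.** Let p be an arm's mortality, D the mean time to death and S the mean stay of survivors. Mean stay in the arm is p × D + (1 − p) × S. With D and S equal in both arms, the difference (A minus B) is (pA − pB) × (D − S).

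**Inputs.** Arm size of 30 is from the synopsis. Everything else is assumed:
- Survivors' stay: lognormal, log-SD 0.6, median 10 or 14 days, so S = 11.97 or 16.76.
- Time to death: exponential, capped at 28 days, median 2, 3, 5 or 7 days, with a late case of 14 days.
- Mortality: 50% against 30%, 45% against 35%, or 40% against 30%.

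**Example.** With 50% against 30% mortality, survivors' median 14 days and deaths' median 3 days:
- Arm A: 0.50 × 4.32 + 0.50 × 16.76 = 10.5 days.
- Arm B: 0.30 × 4.32 + 0.70 × 16.76 = 13.0 days.
- Difference: 0.20 × (4.32 − 16.76) = −2.5 days.

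**Grid.** Difference in mean stay, in days, for a 10-point mortality gap (double it for 20 points):

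| Median time to death | D | Survivors' median 10 | Survivors' median 14 |
|---|---|---|---|
| 2 | 2.89 | −0.91 | −1.39 |
| 3 | 4.32 | −0.77 | −1.24 |
| 5 | 7.06 | −0.49 | −0.97 |
| 7 | 9.47 | −0.25 | −0.73 |
| 14 (late) | 15.15 | +0.32 | −0.16 |

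With median times to death of 2 to 7 days, the range over both gap sizes is −0.25 to −2.78 days. In the late case with a 20-point gap it is −0.32 to +0.64, so the sign can change. If pA = pB and the timing of death is equal, the difference is zero.

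**Single trials of 30 per arm** (20,000 simulated per cell, 2 to 7 day grid):
- The higher-mortality arm shows the shorter mean stay in 55–84% of trials.
- Mann-Whitney on raw stay gives p < 0.05 in 5–23%, and passes the protocol's 0.05/6 threshold in 1–7%.

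**Different assumptions.** With survivors' log-SD 0.5 (median 14 days) and exponential deaths with mean 4 days, simulated mean stay is 9.9 against 12.3 days at 50% against 30% mortality, and 10.5 against 11.7 at 45% against 35%. With deaths spread evenly over days 14 to 28, the direction reverses at 50% against 30%: 18.4 against 17.4 days.

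**Hospital-free days.** In the example, the proportions discharged alive by day 28 are 43.8% and 61.3%, and mean hospital-free days to day 28 are 6.3 and 8.8. The higher-mortality arm now has the worse score. Over the same grid it does so in 72–91% of simulated trials.

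Stay in the emergency department was not quantified.

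**The case against.** Several counter-arguments carry weight.

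- **This may belong in the SAP.** How deaths enter a stay outcome is a derivation rule that an SAP often supplies, and section (10) does not name hospital stay. But the protocol itself fixes the test for all continuous data and confines survival methods to mortality. As written, that covers stay and does not suit it.
- **The large figures need a 20-point mortality gap.** Both arms get the same guideline care and differ only in monitoring, so nothing in the protocol points to 50% against 30%. With 10-point gaps, Mann-Whitney rejects in 5.1–9.4% of trials at 0.05 and 0.8–2.5% at 0.05/6, close to nominal at the lower ends. This stands: a falsely significant result is a minority event.
- **Means may not be reported.** Under these assumptions stay would usually fail the normality test, and medians would be shown. The median moves the same way, by about 2.8 days in the example.
- **Mortality is reported alongside.** That helps a careful reader, but does not correct the estimate for stay or its interval.
- **Raw stay is a fair measure of bed-days used.** True. The fault is in reading it as efficacy, which is the role the protocol gives it.
- **Hospital-free days partly restate mortality.** Also true. The simulation varies only mortality, so the 72–91% is partly built in. In the example 56% and 39% of patients score zero, and Mann-Whitney on this score reaches p < 0.05 in only 8–10% of trials (10-point gaps) or 23–27% (20-point gap). Its merit is that early death cannot count as success, not that it has high power.

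**Conclusion.** The concern holds in its conditional form. If one arm has more deaths and they come before typical discharge, the planned comparison tends to show a shorter stay in that arm. The direction follows from the formula. The size, 0.25 to 2.78 days on the early-death grid and at most 1.39 days for a 10-point gap, rests wholly on assumed distributions and mortality rates. There is no distortion if mortality and timing of death are equal, and it can reverse with late deaths. The primary mortality analysis is unaffected. This is a change worth making rather than a fatal flaw: the result is hard to interpret as efficacy, and the remedy is cheap.

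**What to change.** In section (10) and the matching synopsis text, replace the efficacy comparison of raw total hospital stay with hospital-free days to day 28: 28 minus the days of the index stay, not below 0, with death by day 28 scored 0. Compare the arms by Mann-Whitney, which the plan already names. Alternatively, analyse time to discharge alive with death as a competing event, using cumulative incidence. Handle deaths in the emergency department the same way for emergency department stay. Show raw stay by survival status as description only, which keeps the bed-use information.

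The cost is two or three sentences and a little more analysis. Hospital-free days need only total hospital stay and vital status at day 28, both already collected under section (6). The drawbacks are a less familiar unit than days of stay, and that survivors still in hospital at day 28 score 0, the same as deaths.
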